5 ENDPOINTS

5.1 Efficacy Endpoints

5.1.1 Primary Efficacy Endpoints

The primary efficacy endpoint is the Investigator-assessed ORR per Response Evaluation Criteria in Solid Tumours version 1.1 (RECIST v1.1), defined as the proportion of patients in the response evaluable population who achieve the best overall response (BOR) of complete response (CR) or partial response (PR) (called responders) per RECIST v1.1. The BOR will be categorized as CR, PR, stable disease (SD), progressive disease (PD), or not evaluable (NE). To be qualified as an objective response, CR and PR require confirmation at least 4 weeks after initial observation of such response, and SD requires an observation at least once after 6 weeks. BOR will be evaluated from the start of study treatment.

5.1.2 Secondary Efficacy Endpoints

The secondary efficacy endpoints are:

- PFS assessed by Investigator, defined as the time from the first dose date to the date of first documented progression or death from any cause, whichever occurs first. The documented progression is determined by objective assessment of disease per RECIST v1.1. For patients who are not known to be dead or progressed at time of data cut-off for PFS analysis, the PFS will be censored at the date of the last tumor assessment. Specifically, the following censoring rules will be applied ([Table 2](#)).
 - $\text{PFS (months)} = (\text{date of event [documented progression or death] or date of censoring} - \text{date of first dose} + 1) / (365.25/12)$

Table 2 Censoring Rules for PFS Analysis

Situation	Date	Outcome
No baseline tumor assessments	First dose date	Censored
Death prior to first scheduled tumor assessment	Date of death	Progressed
No post-baseline tumor assessments in absence of death prior to first scheduled tumor assessment	First dose date	Censored
Documented progression	Date of progression	Progressed
Initiation of alternative anti-cancer treatments in absence of documented progression	Date of last tumor assessment prior to initiation of such treatment	Censored
Death or documented progression immediately after missing 2 or more consecutive scheduled tumor assessments	Date of last tumor assessment prior to missed assessments	Censored

- DoR, defined as the time from the date of initial response (CR or PR) to the date of first documented progression per RECIST v1.1 or death from any cause, whichever occurs first. The DoR is calculated only for the responders. For responders who are not known to be dead or progressed at the time of data cut-off for DoR analysis, the DoR will be censored at the date of the last tumor assessment. Specifically, the last 3 situations described in **Table 2** will be applied. The DoR analyses will be performed only if there are enough responders to render the analyses meaningful.
 - $\text{DoR (months)} = (\text{date of event [documented progression or death] or date of censoring} - \text{date of initial response} + 1) / (365.25/12)$
- DCR, defined as the percentage of response evaluable patients who experienced response of CR, PR, or SD for at least 3 months.
- OS, defined as the time from the first dose date to the date of death from any cause. For patients who are not known to be dead at the time of data cut-off for OS analysis, the OS will be censored at the time they are last known to be alive.
 - $\text{OS (months)} = (\text{date of death or date of censoring} - \text{date of first dose} + 1) / (365.25/12)$

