9.13 Post-Treatment Follow-up Visit

The post-treatment follow-up period includes the following:

- Survival follow-up: Patients will be followed via telephone or other electronic contact at approximately 12-week (± 1 week) intervals after the EOTV (or, if no EOTV is conducted, after the decision to end treatment) until LTFU, withdrawal of consent, or death, or until 36 weeks after the last patient's EOTV. Prior to the database lock for final OS analysis, all current survival data will be requested regardless of interval from the prior assessment to collect the most up-to-date survival information for the final OS analysis.
- Tumor assessments: Will be collected every 12 weeks (± 1 week) after the EOTV (or, if no EOTV is conducted, after the decision to end treatment) until evidence of progressive disease (PD), initiation of another anticancer therapy, withdrawal of consent, LTFU, death, or 36 weeks after the last patient's EOTV. Patients who discontinue study treatment due to AEs are followed by radiographic evaluation until PD by RECIST v1.1, if the patients' condition allows. If not, patients will be followed for OS without radiographic evaluation upon the discussion with the Sponsor's Medical Monitor.
- PK and ADA: For patients with evidence of ADA from any prior visit, samples will be collected for PK and ADA at 12 and 24 weeks after the EOTV (or, if no EOTV is conducted, after the decision to end treatment).

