- j Urinalysis (see [Appendix 2](#)) performed at screening, Day 1 of each cycle (with a window of -3 days in relation to the beginning of each cycle), and as clinically indicated.
- k Serum or urine pregnancy test for women of child-bearing potential (with a window of -3 days in relation to the beginning of each cycle).
- l Tumor assessments are performed at the end of Cycle 2 (with a window of -3 days in relation to the beginning of the next cycle), and at the end of every 3 cycles (Cycles 5, 8, 11, etc.) thereafter (with a window of -7 days in relation to the beginning of the next applicable cycle) until treatment discontinuation. Patients who discontinue from study treatment should be assessed every 12 weeks (± 1 week) after the EOTV (or, if no EOTV is conducted, after the decision to end treatment) until evidence of PD, initiation of another anticancer therapy, withdrawal of consent, LTFU, death, or 36 weeks after the last patient's EOTV. EOTV tumor assessment does not need to be conducted if prior tumor assessment was performed within 28 days of the EOTV and results are available for RECIST assessments. Patients who discontinue study treatment due to AEs are followed by radiographic evaluation until PD by RECIST v1.1, if the patients' condition allows. If not, patients will be followed for OS without radiographic evaluation upon the discussion with the Sponsor's Medical Monitor.
- m Survival follow-up occurs every 12 weeks (± 1 week) after the EOTV (or, if no EOTV is conducted, after the decision to end treatment) until withdrawal of consent, LTFU, death, or 36 weeks after the last patient's EOTV.

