3.1 Overall Study Design and Plan

This is a Phase 2, open label, non-randomized study in the first-line treatment of patients with recurrent or metastatic SCCHN not curable by local therapy, with no prior systemic therapy for SCCHN in the recurrent or metastatic setting (with the exception of systemic therapy completed > 6 months prior if given as part of multimodal treatment for locally advanced disease).

Approximately 80 patients will be enrolled in 2 cohorts, as shown in **Figure 1**, to receive enoblituzumab in combination with either retifanlimab (Retifanlimab Cohort, PD-L1 positive [CPS \geq 1] patients, N=50) or tebotelimab (Tebotelimab Cohort, PD-L1 negative [CPS < 1] patients, N=30). Enrollment into each cohort will occur in a non-randomized fashion. Patients may not crossover between cohorts. PD-L1 expression will be prospectively collected and prospectively analyzed. B7-H3 and LAG-3 expression will be prospectively collected and retrospectively analyzed.

Figure 1

Study Schema

[figure not shown]
Enrollment in the 2 study cohorts will occur independently in a non-randomized fashion

Dosing Regimens:
 Enoblituzumab: 15 mg/kg Q3W
 Retifanlimab: 375 mg Q3W
 Tebotelimab: 600 mg Q3W

Efficacy Outcomes
Primary: ORR
Secondary: PFS, DCR, DoR, OS

Patients will receive the assigned study drugs (enoblituzumab 15 mg/kg and either retifanlimab 375 mg or tebotelimab 600 mg) on a every 3 weeks (Q3W) basis, in cycles of 3 weeks duration (see **Figure 2**). The initial tumor assessment will occur at the end of Cycle 2 (i.e., after approximately 6 weeks), and at the end of every 3 cycles thereafter (i.e., approximately every 9 weeks). After receipt of the last dose of study treatment, patients will enter an Efficacy Follow-up Period and will be followed for survival.

Figure 2

An independent Data Safety Monitor (DSM), the Sponsor, and Investigators will maintain regular oversight of patient safety throughout the trial. In the Tebotelimab Cohort, toxicity will be evaluated by monitoring the occurrence and severity of DLTs in the first 12 patients (2 mini-cohorts of 6 patients each) through Cycle 2 Day 7.

The data for each of the Retifanlimab and Tebotelimab Cohorts will be analyzed upon completion of enrollment of each cohort, and after all patients in the applicable cohort have at least one tumor assessment, to inform whether to proceed with the study and to determine any modifications to the trial design.

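### Row 3 of the PFS censoring table censors at first dose a never-scanned patient who dies after missing one assessment, in conflict with row 2 and the PFS definition

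*SAP*

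**What the plan says.** SAP Section 5.1.2 measures PFS to the "date of first documented progression or death from any cause, whichever occurs first". Its general censoring sentence covers only patients not known to have died or progressed. Table 2 then gives the specific rules. Four rows matter here:

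- **Row 2:** "Death prior to first scheduled tumor assessment" is an event on the date of death.
- **Row 3:** "No post-baseline tumor assessments in absence of death prior to first scheduled tumor assessment" is censored at the first dose date.
- **Row 5:** "Initiation of alternative anti-cancer treatments in absence of documented progression" is censored at the last tumor assessment before that treatment.
- **Row 6:** "Death or documented progression immediately after missing 2 or more consecutive scheduled tumor assessments" is censored at the last assessment before the missed ones.

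Protocol Section 14.6.3, Table 7, has the same rows. PFS is analysed in the Safety Population (SAP Section 4), so patients never scanned after baseline are included.

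SAP Section 3.1 puts the first on-treatment scan at about week 6 and later ones about every 9 weeks, so the second falls at about week 15. After treatment stops, Protocol Section 9.13 says tumor assessments "Will be collected every 12 weeks", counted from the end of treatment visit (EOTV) or, without one, from the decision to stop. Protocol Appendix 1 also schedules an EOTV scan, with one exemption: "EOTV tumor assessment does not need to be conducted if prior tumor assessment was performed within 28 days of the EOTV".

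**The concern.** The exception in row 3 ends at the first scheduled scan, while row 6 starts to discard deaths only at the second consecutive missed one. A never-scanned patient who dies between those two points is caught by row 3 alone. The death is known and is counted for OS, but for PFS the patient leaves the risk set on Day 1.

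Such patients are plausible. Clinical progression is a reason for stopping treatment separate from objective progression (Protocol Section 4.4). Symptomatic deterioration is not an objective response (Protocol Appendix 4). Failure to attend the EOTV is not a deviation (Protocol Section 9.12).

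The error runs in one direction. It removes early deaths and so raises the PFS curve, and there is no control arm in which the same rule would operate.

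**Working it through.** **Step 1: apply the rows.** Take a patient with a baseline scan, no post-baseline scan and no new anticancer therapy, on the on-treatment schedule, with scans due at about Day 43 (week 6) and Day 106 (week 15). The SAP formula is PFS in months = (date − first dose date + 1)/(365.25/12), so an event on Day d gives d/30.4375.

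| Death | Scheduled scans missed | Rows that fit | PFS result |
|---|---|---|---|
| Day 38 | 0 | 2 | 38/30.4375 = 1.25 months, event |
| Day 50 | 1 | 3 only | 1/30.4375 = 0.03 months, censored |
| Day 75 | 1 | 3 only | 0.03 months, censored |
| Day 130 | 2 | 3 and 6 | censored |

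Counted as an event, the Day 50 death would give 50/30.4375 = 1.64 months and the Day 75 death 75/30.4375 = 2.46 months.

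**Step 2: compare with row 6.** A patient scanned at week 6 who misses week 15 and dies at week 20 has missed one assessment. No censoring row matches, so the definition makes this an event. The never-scanned patient who dies on Day 50 has also missed one assessment but is censored.

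**Step 3: size.** The documents give no rate for such deaths, so their number k is an assumption. For the other patients, assume exponential PFS with a median of 3.2 months, the figure for pembrolizumab monotherapy at CPS ≥ 1 in Protocol Section 2.2. Then S(6) = exp(−6 ln2/3.2) = 0.2726.

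A patient censored on Day 1 contributes nothing, so row 3 yields S(6). With the k deaths counted, all before month 6, 6-month PFS is ((n − k)/n) × S(6).

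| n | k | Deaths counted | Row 3 as written | Overstatement (points) |
|---|---|---|---|---|
| 50 | 1 | 0.267 | 0.273 | 0.5 |
| 50 | 2 | 0.262 | 0.273 | 1.1 |
| 50 | 3 | 0.256 | 0.273 | 1.6 |
| 50 | 5 | 0.245 | 0.273 | 2.7 |
| 30 | 1 | 0.264 | 0.273 | 0.9 |
| 30 | 2 | 0.254 | 0.273 | 1.8 |
| 30 | 3 | 0.245 | 0.273 | 2.7 |

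A count in whole patients agrees. At n=50 with 36 events by month 6, dropping one death moves 14/50 = 28.0% to 14/49 = 28.6%. At n=30 with 22 events, it moves 8/30 = 26.7% to 8/29 = 27.6%.

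**Step 4: compare with sampling error.** The 95% half-width is 1.96 × √(0.2726 × 0.7274/n), which is 12.3 points at n=50 and 15.9 at n=30.

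The median is a poorer gauge. With scans simulated at weeks 6, 15, 24 and so on (n=50), it was unchanged in about 90% of replicates at k=1 and 73% at k=5.

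**The case against.** **The window depends on the patient's schedule.** This stands. A patient who stops at Day 22, has no EOTV and dies on Day 50 has a first applicable scan at about Day 22 + 84 = Day 106. On that reading the death precedes the first scheduled assessment and row 2 makes it an event. A reader might infer that every never-scanned death in weeks 6 to 15 is lost. The documents do not support that. The gap holds mainly patients still on treatment at week 6 who missed that scan, or who attended an EOTV without one. The SAP does not say whether the first scheduled assessment is fixed at week 6 or counted per patient, so the wording needs settling either way.

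**The general sentence already limits censoring to patients not known to be dead.** This helps only in part. Row 6 shows that the table deliberately reaches known deaths, so a programmer cannot assume that row 3 spares them.

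**The conflict with row 6 is inferred.** It is: no row says that a death after one missed scan is an event. That follows from the definition together with row 6's threshold. The conflict with row 2 is direct and does not need it.

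**The effect is negligible.** It is small, on a secondary descriptive endpoint with no test attached. That limits the weight of the point but does not make the rule coherent.

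**Conclusion.** The inconsistency is real in both tables. For a never-scanned patient with a baseline scan and no new therapy, row 3 turns a known death after one missed assessment into a Day 1 censoring. This contradicts row 2 and the PFS definition, and by implication row 6.

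The bias is upward and small: about 0.5 to 0.6 points of 6-month PFS per such patient at n=50 and about 1 point at n=30. These figures rest on an assumed number of patients and an assumed 3.2-month median, which for the Tebotelimab Cohort is borrowed from a CPS ≥ 1 population. They lie well inside sampling error.

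Two stronger conclusions might be drawn, and neither is supported. One is that any departure from counting all deaths is an error. Row 6 departs by design, and the fault is only that row 3 does not fit with its neighbours. The other is that the trial's efficacy conclusions are at risk. ORR is analysed separately, OS counts every death, and DoR applies only to responders, who by definition have been scanned.

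**What to change.** In both SAP Table 2 and Protocol Table 7:

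1. In rows 2 and 3, replace the first scheduled assessment by the second. A never-scanned patient who dies after fewer than two missed scheduled assessments is then an event on the date of death.
2. State that scheduled assessments are counted on the patient's applicable schedule: on treatment, EOTV, or 12-weekly follow-up.
3. Leave never-scanned deaths after two or more missed assessments censored at first dose under row 3, consistent with row 6.
4. State that row 1 (no baseline scan) and row 5 (new anticancer therapy) take precedence over the changed row 2. Without this, the wider row 2 would overlap both with the opposite outcome.
5. For row 5 with no post-baseline scan, give the first dose date as the censoring date. Otherwise the last assessment is the baseline scan, which Protocol Appendix 4 allows up to 4 weeks before treatment: (−28 + 1)/30.4375 = −0.89 months.

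Row 4 still governs where progression is documented before death, since the definition takes whichever comes first.

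The cost is a few words in two tables and minor programming. The count of missed assessments is already needed for row 6, and death dates are collected for OS. PFS may come out slightly less favourable.

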4.4 Study Treatment Discontinuation

Patients who tolerate treatment may continue to receive treatment with the study drug(s) as specified in the protocol until any one of the following conditions are met:

- Adverse Event Requiring Treatment Discontinuation
 - Patients who discontinue study treatment due to AEs are followed by radiographic evaluation until disease progression by RECIST v1.1, if the patients' condition allows. If not, patients will be followed for OS without radiographic evaluation upon the discussion with the Sponsor's Medical Monitor.
- Completed Treatment per Protocol
- Death
- Physician Decision (should occur only after discussion with the Sponsor's Medical Monitor)

- Lost to Follow-up
- Pregnancy
- Progressive Disease-Clinical Progression
- Progressive Disease-Objective Progression
 - Patients who have radiographic progression according to RECIST v1.1 may remain on study treatment until the next scheduled radiographic evaluation if the following conditions are met:
 - Absence of clinical symptoms or signs indicating clinically significant disease progression.
 - No decline in ECOG performance status.
 - Absence of rapid disease progression or threat to vital organs or critical anatomical sites (e.g., CNS metastasis, respiratory failure due to tumor compression, spinal cord compression) requiring urgent alternative medical intervention.
 - No significant, unacceptable, or irreversible toxicities related to study treatment.
- Major Protocol Deviation Requiring Treatment Discontinuation
- Study Terminated (patients might be offered enrollment in a follow-up/roll over protocol if in place at the time of study termination)
- Patient Decision
- Patient Withdrew Consent for Study

If the Investigator decides that the patient should be withdrawn from the study or from dosing for any reason other than disease progression, the Sponsor or its designee must be alerted within 24 hours).

A patient may be determined to be lost to follow up (LTFU) after there have been 3 documented phone contact attempts. If this fails, a certified letter should be sent to the patient. Only after these attempts have failed can a patient be determined to be LTFU.

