9.12 End of Treatment Visit

The end of treatment visit (EOTV) should be performed within 30 days after the patient has met study treatment discontinuation criteria, and before initiation of any subsequent anticancer therapies.

It is recognized that patients may go to other facilities for continuing care, or may elect not to return to the study site. Therefore, failure to return for an EOTV will not be considered a protocol deviation. Whenever possible all required procedures and tests should be performed, with the following exception: the EOTV tumor assessment does not need to be conducted if prior tumor assessment was performed within 28 days of the EOTV and results are available for RECIST assessments.

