14.6.3 Time-to-Event Endpoints and Analyses

The time-to-event efficacy endpoints include the Investigator-assessed PFS, DoR, and OS as defined below.

Progression-free survival (PFS) will be defined as the time from the first dose date to the date of first documented progression or death from any cause, whichever occurs first. The documented progression is determined by objective assessment of disease per RECIST v1.1. For patients who are not known to be dead or progressed at the time of data cut-off for PFS analysis, the PFS will be censored at the date of the last tumor assessment. Specifically, the following censoring rules will be applied ([Table 7](#)).

Table 7 Censoring Rules for PFS

Situation	Date	Outcome
No baseline tumor assessments	First dose date	Censored
Death prior to first scheduled tumor assessment	Date of death	Progressed
No post-baseline tumor assessments in absence of death prior to first scheduled tumor assessment	First dose date	Censored
Documented progression	Date of progression	Progressed
Initiation of alternative anti-cancer treatments in absence of documented progression	Date of last tumor assessment prior to initiation of such treatment	Censored
Death or documented progression immediately after missing 2 or more consecutive scheduled tumor assessments	Date of last tumor assessment prior to missed assessments	Censored

Duration of Response (DoR) is defined as the time from the date of initial response (CR or PR) to the date of first documented progression or death from any cause, whichever occurs first. The DoR is calculated only for the responders. For responders who are not known to be dead or progressed at the time of data cut-off for DoR analysis, the DoR will be censored at the date of the last tumor assessment. Specifically, the last 3 situations described in **Table 7** will be applied. The DoR analyses will be performed only if there are enough responders to render the analyses meaningful.

Overall survival (OS) is defined as the time from the first dose date to the date of death from any cause. For patients who are not known to be dead at the time of data cut-off for OS analysis, the OS will be censored at the time they are last known to be alive.

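### The PFS and DoR censoring rule for new therapy removes patients who stopped for clinical progression, which biases PFS upward by an unknown amount, and no sensitivity analysis would show how far

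*SAP*

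**What the plan says.** **Events.** PFS and DoR count RECIST progression or death. SAP 5.1.2 states: "The documented progression is determined by objective assessment of disease per RECIST v1.1".

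**Censoring.** One row of SAP Table 2 covers "Initiation of alternative anti-cancer treatments in absence of documented progression". The date, the same in protocol Table 7 (section 14.6.3), is "Date of last tumor assessment prior to initiation of such treatment". Another row, "No post-baseline tumor assessments in absence of death prior to first scheduled tumor assessment", censors at first dose. For DoR, "the last 3 situations described in Table 2 will be applied"; these include the new-therapy row.

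**Stopping treatment.** Protocol 4.4 lists "Progressive Disease-Clinical Progression" separately from objective progression.

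**Scanning.** Scans fall at about week 6 and then about every 9 weeks (SAP 3.1). After treatment they continue until progression or, among other reasons, "initiation of another anticancer therapy, withdrawal of consent, LTFU, death, or 36 weeks after the last patient"'s EOTV (protocol 9.13).

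**Safeguards.** Protocol 9.12 places the end-of-treatment visit (EOTV) within 30 days of meeting the stopping criteria and before any new therapy, and Appendix 1 includes a tumor assessment at that visit. However, "failure to return for an EOTV will not be considered a protocol deviation", and the scan is waived if one was done in the previous 28 days. Appendix 4 asks sites to try to document objective progression after treatment stops.

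**Analysis.** SAP 6.7.2 reports Kaplan-Meier medians and 6- and 12-month PFS rates. It contains no alternative to Table 2.

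**The concern.** Kaplan-Meier assumes that a censored patient has the same future risk as those still being followed. A patient who stops for clinical progression and moves to another therapy is censored because the disease is getting worse. Dating the censoring back to the last scan removes the patient from the risk set before the deterioration, and the curve then gives that patient the prognosis of people still progression-free. The PFS curve is therefore too high.

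Both cohorts are single-arm, so no control arm carries the same bias. Any reading of PFS will be against outside figures, such as the pembrolizumab results in protocol 2.2. As the SAP stands, a reader of the report could not tell how many patients were censored this way or how much the estimates depend on it.

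**Working it through.** **1. The plan's own figure.** SAP 3.2 has no planning figure for PFS or DoR. Its power statement concerns ORR in the Retifanlimab Cohort. Exact binomial: P(X ≥ 14 | n = 50, p = 0.36) = 0.9097 and P(X ≥ 14 | n = 50, p = 0.19) = 0.0791. These reproduce the stated 91% and 0.079, and this point does not affect them.

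**2. How a patient falls through.** Suppose the week 6 scan is stable, the patient worsens clinically at week 9, attends the EOTV and starts new therapy at week 10. The week 6 scan is 21 days before a week 9 EOTV, so the EOTV scan may be waived. PFS is censored at week 6. If the patient worsens at week 12, the last scan is 42 days old and the waiver does not apply; the gap then needs a missed visit or scan.

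**3. Inputs for size.**
- Scan grid: weeks 6, 15, 24, which is 42, 105, 168 days ÷ 30.4375 = 1.38, 3.45, 5.52 months; the next scan is at 7.59.
- Assumed true median m = 3.2 months, the pembrolizumab monotherapy PFS median for CPS ≥ 1 in protocol 2.2; 5.0 months is used as a second case.
- Share f of failures that are clinical progression followed by new therapy without RECIST progression: 5 to 30%. This is an assumption; the documents give no value.
- Exponential failure times, also an assumption.

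**4. Closed form, progressions only, m = 3.2, f = 10%, no progression documented at the EOTV.** Let F(t) = 1 − 0.5^(t/m). At the three scans F = 0.2584, 0.5263, 0.6975. The interval probabilities p are 0.2584, 0.2680, 0.1712. Under Table 2, the risk set at each scan is 1 − F(previous scan) − f·p, and the events are (1 − f)·p.
- Week 6: 0.2326 / 0.9742 = 0.239, so S = 0.761.
- Week 15: 0.2412 / 0.7148 = 0.337, so S = 0.5045.
- Week 24: 0.1541 / 0.4566 = 0.337, so S = 0.334, which is also the 6-month value.

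Counting clinical progression as an event on its own date, with F(6) = 0.7274: S(6) = 1 − (0.9 × 0.6975 + 0.1 × 0.7274) = 0.2995. The excess is 33.4 − 30.0 ≈ 3.5 points.

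**5. Simulation.** 200,000 patients, same grid, m = 3.2, 24-month cut-off, and 10% of the other failures are deaths on their own date. Rates in %.

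| f | 6-month, Table 2 vs event | Excess | Excess if EOTV scan documents PD in half | 12-month, Table 2 vs event | Median (months), Table 2 vs event |
|---|---|---|---|---|---|
| 5% | 31.5 vs 29.8 | 1.7 | 0.8 | 8.6 vs 7.7 | 3.45 vs 3.45 |
| 10% | 33.0 vs 29.5 | 3.5 | 1.6 | 9.7 vs 7.8 | 3.84 vs 3.45 |
| 20% | 36.9 vs 29.5 | 7.4 | 3.4 | 12.1 vs 7.8 | 5.52 vs 3.45 |
| 30% | 40.9 vs 29.1 | 11.8 | 5.3 | 15.1 vs 7.7 | 5.52 vs 3.45 |

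The 12-month and median columns are the case with no progression documented at the EOTV. With half documented, the Table 2 median is 3.45, 3.45, 3.66 and 4.36 months. With m = 5.0 the 6-month excess without EOTV documentation is 1.7, 3.5, 7.4 and 11.7 points. In repeated samples of 50 patients (m = 3.2), the mean excess at f = 10, 20, 30% is 3.4, 7.3 and 11.8 points.

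**6. Patients with no post-baseline scan.** F(1.38) = 26% of failures occur before the week 6 scan. Any of these that take this path without a scan are censored at first dose and add nothing to the curve.

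**7. DoR.** Take the median of 23.4 months from protocol 2.2 and a constant hazard, with clinical progressions censored on their own date: S(12) = 0.5^(12(1 − f)/23.4). This moves from 70.1% at f = 0 to 71.3, 72.6, 75.2 and 78.0% at f = 5, 10, 20, 30%.

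**The case against.** The strongest reply is that the protocol already plans a scan at the point where it is needed. The EOTV comes before new therapy, and where its scan shows RECIST progression the patient is an event. The no-documentation column is therefore an upper case, and the half-documented column shows how quickly the excess shrinks. This stands for size. It does not remove the mechanism, because the visit can be missed, the scan can be waived, and scanning ends at new therapy. Since 9.12 already asks for the required procedures where possible, rewording it would add little.

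It is also fair that this is a common convention, that PFS and DoR are two of four secondary efficacy endpoints listed without ranking, and that no PFS test or threshold is planned. An approximate 95% half-width for a 6-month rate near 30% is 1.96 × √(0.3 × 0.7/50) = 13 points with 50 patients and 16 with 30, so a bias of 2 to 4 points sits well inside the sampling error. But the interval will be centred on the biased value and does not reflect the bias.

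Three stronger readings are tempting and not supported:
- *That median PFS must be inflated.* The median moves in steps on the scan grid. In the progressions-only model the curve at week 15 is 47.4% at f = 0 and 50.45% at f = 10%, so it crosses one half by under half a point. With some deaths the median is 3.84 months, and with half the progressions documented at the EOTV it does not move at 10%.
- *That deaths are lost.* Death before the first scheduled scan is a PFS event, and every death counts in OS. The gap is a death after new therapy in a patient already censored by the new-therapy row.
- *That DoR is distorted to the same degree.* A confirmed responder has post-baseline scans, so censoring at first dose cannot arise, and DoR is analysed only if there are enough responders.

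**Conclusion.** The point holds as a gap in the analysis plan. The rule is clear and identical in both documents, and the censoring it produces is informative and biases PFS upward. DoR is biased in the same direction, to a smaller and less certain extent. ORR, OS and the 14-of-50 rule are unaffected.

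The direction is secure; the size is not. It rests on the assumed 3.2-month median, exponential failure, and above all the share taking this path and how often the EOTV scan documents progression, neither of which the documents give. Across shares of 5 to 30%, the 6-month PFS excess runs from about 1 to 12 points. At the low end this is trivial; at the high end it would change how the PFS result reads against an outside benchmark. Only the trial's own censoring counts can tell which applies, and the plan does not call for them.

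**What to change.** Keep Table 2 as the primary rule. In SAP 6.7.2 add, for PFS and DoR:
1. A sensitivity analysis that counts treatment discontinuation for clinical progression as an event on that date.
2. A second analysis, labelled conservative, that also counts the start of new anticancer therapy without documented progression as an event, and counts deaths after new therapy where no earlier event exists. State that it overcounts, because it includes patients who stopped for an adverse event or by choice while progression-free.
3. A table of the number of patients censored under each Table 2 row, by cohort.

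The data are already needed elsewhere: discontinuation reason (SAP 6.3.1), the date of the decision to stop (SAP 6.4), and the start of subsequent therapy (Table 2 itself). No new visits or scans are required. The cost is a short SAP addition and a few outputs per cohort. The sensitivity estimates will be less favourable than the primary ones, and the second is biased downward, so the truth should be read as lying between it and the Table 2 result. Specify this before results are known.
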